2.7.1.5 Proportion of patients with prescription of biologic treatment

The proportion of patients with any prescription of biologic therapy during the on-treatment period will be presented. Events which occur during on-treatment period will be included.

2.7.1.6 Summary of change from baseline of daytime and nighttime symptom scores by 4-week intervals during on-treatment period

The daytime and night time symptom scores will be collected using validated electronic patient diary. Scoring of measures: A range of response categories for each question from 0 to 6 (0 – totally controlled, 6 – extremely poorly controlled) is used in the daytime asthma symptom scale. Response categories ranging from 0 (indicating no awakening with asthma symptoms) to 3 (indicating awake all night) are used in the nocturnal diary scale. Daily daytime symptom scores will be computed as the average of the available scores on four questions on the daytime symptom scale.

The mean daytime asthma symptom scores/nighttime symptom score will be calculated for each patient for each 4 week visit interval and over on-treatment period. The average score for each time interval is defined as the sum of daily scores (based on all the available questions) divided by the number of days where diary records have been made on nighttime/daytime score for that visit interval. The non-missing data within each 4 week interval in treatment period will be used to calculate the mean value, as long as there are at least 14 days with non-missing e-diary data (based on all the available questions) in a 4-week period. Otherwise, the value will be set as missing.

2.7.2 Statistical hypothesis, model, and method of analysis

The analysis of all secondary endpoints will be based on on-treatment data (that is from first dose of study treatment till last dose of study treatment + 1).

The proportion of patients with no SCS use during on-treatment will be summarized by treatment groups.

The proportion of patients requiring ≥ 7.5 mg systemic corticosteroid dose in mg prednisone/prednisolone (or equivalent) per day continuously for at least 30 days within the on-treatment period will be summarized by treatment in overall population.

AQLQ+12, ACQ-5 and change from baseline in daytime and nighttime score will be summarized by treatment for all visits. All the summaries will be based on observed on-treatment data and non-imputed data.

2.7.3 Handling of missing values/censoring/discontinuations

No imputation will be done for secondary endpoints.

2.8 Safety analyses

All safety data will be summarized for the safety set. Safety summaries will be primarily based on on-treatment data with selected tables also presented for all data after the first intake of study drug, while all safety data will be listed.

2.8.1 Adverse events (AEs)

Adverse events after informed consent including asthma exacerbations will be listed.

Adverse events starting on or after the day of the first intake of study drug and until 7 days after the last intake of study drug will be classified as treatment emergent adverse events. Adverse events that started during the study after informed consent and before the day of the first intake of study drug will be classified as prior adverse events and not included in tabulations of treatment emergent adverse events.

The number and percentage of patients who reported TEAEs will be summarized by primary system organ class (SOC), preferred term (PT), and treatment group for

- all adverse events (AEs)
- all AEs by maximum severity
- AEs suspected to be related to study drug
- AEs by standardized MedDRA query (SMQ) level serious AEs (SAEs)
- AEs leading to permanent study drug discontinuation
- Serious adverse events

Unless otherwise specified, primary system organ classes will be sorted alphabetically and, within each primary system organ class, the preferred terms will be sorted in descending order of frequency in the QAW039 150 mg once daily treatment group. If a patient reported more than one AE with the same preferred term, the AE will be counted only once. If a patient reported more than one AE within the same primary system organ class, the patient will be counted only once at the system organ class level.

In addition, the most frequent AEs will be presented by preferred term in descending order of frequency in the QAW039 150 mg once daily treatment group.

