	
 • H₀₄ 150 overall population: the distribution of the total SCS dose (in mg) in Fevipiprant 150 mg QD plus SoC is equivalent to the distribution of the total SCS dose (in mg) in placebo plus SoC for the overall population 
The familywise type I error rate will be controlled at the two-sided 5% level across the primary null hypotheses using graphical approach. The total systemic corticosteroid dose in mg prednisone/prednisolone (or equivalent) over 52 weeks of treatment will be analyzed using the Wilcoxon-Mann-Whitney rank sum test (Van Elteren test). For overall population analysis will be stratified by randomization stratum – blood eosinophils levels (≥ 250 cells/μl and < 250 cells/μl). For subgroup with blood eosinophils ≥ 250 cells/μl, analysis will not include stratification factor. The summary statistics for total SCS dose by treatment group will be provided. The total SCS dose data will be aggregated into monthly data for analysis. For the patients discontinuing treatment early, the total SCS dose for 52 weeks will be obtained as annualized SCS dose. For example if patient took 280 mg for 7 months then for 12 months patient will be taking $280 \times 12/7 = 480$mg total SCS dose. Efficacy data collected during the use of biologics will be set to missing, since use of biologics can confound efficacy data. After replacing SCS dose with missing, patient will not have data available for all 12 months, thus total SCS dose will be obtained as annualized dose.
 
Secondary analysis:
 
The proportion of patients with free of SCS use over 52 weeks treatment will be summarized by treatment and analyzed using logistic regression in overall population. The model will include treatment and randomization strata as covariates.
 
The proportion of patients requiring ≥ 7.5mg systemic corticosteroid dose in mg prednisone/prednisolone (or equivalent) per day continuously for at least 30 days in 52 weeks treatment period will be summarized by treatment and analyzed using logistic regression in overall population. The model will include treatment and randomization strata as covariates.
 
The AQLQ+12 and ACQ-5 score will be analyzed using a MMRM with an unstructured covariance structure with factors for treatment group, time and randomization stratum, as well as the baseline values as continuous linear covariates.
 
The time to first prescription of biologic therapy from first dose of study treatment received over 52 weeks of treatment will be summarized by treatment group. Between-treatment differences will be evaluated using cox regression model.
 
Change from baseline in each endpoint (daytime and nighttime symptom score) will be analyzed using mixed models repeated measures (MMRM) model with factors as treatment group, randomization strata, time interval, time interval by treatment group interaction and the associated baseline as continuous linear covariate.
 
Safety analysis will be based on safety set and analysis will be presented by treatment group. Safety summaries will be provided based on on-treatment data. The on-treatment period lasts from the date of first administration of study treatment to 14 days after the date of the last actual administration of any study treatment.

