9.5.2 Safety variables

For all safety analyses, the safety set will be used. All listings and tables will be presented by treatment group.

Safety summaries (tables, figures) include only data from the on-treatment period with the exception of baseline data which will also be summarized where appropriate (e.g. change from baseline summaries). In addition, a separate summary for death including on treatment and post treatment deaths will be provided. In particular, summary tables for adverse events (AEs) will summarize only on-treatment events, with a start date during the on-treatment period (treatment-emergent AEs).

The on-treatment period lasts from the date of first administration of study treatment to 14 days after the date of the last actual administration of any study treatment.

Adverse events

All information obtained on adverse events will be displayed by treatment group and subject.

The number (and percentage) of subjects with treatment emergent adverse events (events started after the first dose of study medication or events present prior to start of double-blind treatment but increased in severity based on preferred term) will be summarized in the following ways:

- by treatment, primary system organ class and preferred term.
- by treatment, primary system organ class, preferred term and maximum severity.
- by treatment, Standardized MedDRA Query (SMQ) and preferred term

Separate summaries will be provided for study medication related adverse events, death, serious adverse events, other significant adverse events leading to discontinuation and adverse events leading to dose adjustment.

The adverse events of special interest will be listed and summarized by treatment group.

A subject with multiple adverse events within a primary system organ class is only counted once towards the total of the primary system organ class.

Vital signs

All vital signs data will be listed by treatment group, subject, and visit and if ranges are available, abnormalities will be flagged. Summary statistics will be provided by treatment group.

12-lead ECG

All ECG data will be listed by treatment group, subject and visit, abnormalities will be flagged. Summary statistics will be provided by treatment.

Clinical laboratory evaluations

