This statistical analysis plan (SAP) describes all planned analyses for the Clinical Study Report (CSR) of study QAW039A2323, a 52-week phase IIIb, multicenter, randomized, double-blind, double-dummy, parallel-group, placebo-controlled study of fevipiprant once daily plus standard-of-care (SoC) for reduction of systemic corticosteroids (oral and parenteral) use in patients with severe asthma.

[figure not shown]
The content of this SAP is based on protocol QAW039A2323 version 01.

Data will be analyzed by Novartis or a contracted contract research organization (CRO) according to the data analysis section 9 of the study protocol which is available in [Appendix 16.1.1 of the CSR](#). Important information is given in the following sections and details will be provided, as applicable, in [Appendix 16.1.9 of the CSR](#).

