ACQ-5	Baseline ACQ-5 score is defined as ACQ-5 scores obtained on Day 1. If the ACQ-5 score on Day 1 is missing then the last available ACQ-5 score prior to Day 1 will be used. If the ACQ-5 score is missing on Day 1 and on all visits before Day 1, the respective baseline value will be set to missing.	ACQ assessments are taken during screening and on day 1.
e-Diary daytime and night time asthma symptoms	For e-diary data (daytime and night time asthma symptoms) which are collected daily, the mean score for the baseline is calculated from Visit 101 to Day 1) will be considered as the baseline mean score. The non-missing data within that interval will be used to calculate the mean value	Note that the morning assessment for Day 1 counts towards the baseline (as a part of run-in). However, the evening assessment for Day 1 counts as the treatment period (not as a part of run-in).

	
as long as there are at least 75% days in the period with non-missing e-diary data. Since these measurements are collected at both morning and evening at Day 1, the morning assessment for Day 1 counts towards the baseline (as a part of run-in) while the evening assessment counts as the treatment period.
	
--	---	--

Post-baseline measurement

Post baseline measurements are defined as those assessments after the start of study treatment.

Change from baseline

When change from baseline is of interest, the following formula will be used for each scheduled visit and time-point where baseline and post-baseline values are both available:

Change from baseline = post-baseline value – baseline value; and

If baseline or post-baseline values are missing, then the change from baseline will be missing.

On-treatment assessment/event and observation periods

The overall observation period will be divided into three mutually exclusive segments:

1. **pre-treatment period:** from day of patient’s informed consent to the day before first administration of study treatment
2. **on-treatment period:** from date of first administration of study treatment to date of last actual administration of any study treatment (including start and stop date)
3. **post-treatment period:** starting at day 1 after last administration of study treatment.

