Safety summaries (tables, figures) include data from the pre-treatment period (to display the baseline status e.g. for ECG) and the on-treatment period. Data from the post-treatment period with the exception of deaths should not be included unless requested from Health Authorities or external committees.

In particular, summary tables for adverse events (AEs) will summarize only on-treatment events, with a start date during the on-treatment period, the so-called **treatment-emergent** AEs.

However, all safety data (including those from the post-treatment period) will be listed and those collected during the pre-treatment and post-treatment period are to be flagged.

Visit remapping and assessment windows

If a scheduled visit did not occur, then the data from the treatment discontinuation or study discontinuation visit may be used as the data from the scheduled visit. This is done if the treatment discontinuation or study discontinuation visit occurred closer to the planned study day of the missing scheduled visit than to the planned study day of any other scheduled visit. In this case the treatment discontinuation or study discontinuation visit will be treated as the scheduled visit for the purpose of all analyses so that no missing data imputation will be necessary. Otherwise the data from any scheduled visit that did not occur will be dealt with like any other missing data. If the treatment discontinuation or study discontinuation visit is not re-mapped to any scheduled visit, it will be treated as an unscheduled visit that does not appear in by-visit summaries.

Last contact date

The maximum of the date of last visit, date of last epoch completion, date of withdrawal of consent would be the date of last contact for the patient participating in the study.

The last contact date is defined as the latest complete date from the above list or the cut-off date whichever comes first. The cut-off date will not be used for last contact date, unless the patient was seen or contacted on that date. No date post cut-off date will be used. Completely imputed dates (e.g. the analysis cut-off date programmatically imputed to replace the missing end date of a dose administration record) will not be used to derive the last contact date.

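### Treatment-emergent adverse events have three different end dates (last dose, +7 days, +14 days), none is given precedence, and the departure from the protocol's 14 days is not declared

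*SAP*

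**What the plan says.** Three places attach an end date to the term treatment-emergent.

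- **Protocol 9.5.2.** "Safety summaries (tables, figures) include only data from the on-treatment period", with baseline data and a separate summary of deaths as additions. The period runs "to 14 days after the date of the last actual administration of any study treatment", and treatment-emergent events are those that start within it. The data analysis part of the protocol summary gives the same 14 days.
- **SAP 2.1.1.** The on-treatment period runs "from date of first administration of study treatment to date of last actual administration of any study treatment (including start and stop date"), and the post-treatment period begins the next day. Adverse event tables "will summarize only on-treatment events, with a start date during the on-treatment period", and the SAP calls these events treatment-emergent. It adds: "Data from the post-treatment period with the exception of deaths should not be included unless requested from Health Authorities or external committees".
- **SAP 2.8.1.** Events with onset from first intake and "until 7 days after the last intake of study drug will be classified as treatment emergent adverse events".

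Other SAP safety sections set their own limits: 7 days for laboratory data (2.8.3), 7 days for vital signs (2.8.4.2) and 1 day for ECG (2.8.4.1). The main deaths summary also uses 7 days (2.8.2), but all deaths after first dose are tabulated as well.

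The SAP introduction says the data will be analyzed "according to the data analysis section 9 of the study protocol". SAP Section 4, which records changes from the protocol, covers only the primary endpoint (unchanged) and the secondary endpoints (now descriptive).

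**The concern.** There are two separate faults. First, the SAP contradicts itself: 2.1.1 and 2.8.1 give different rules for the same tables. Second, neither rule matches the protocol section that the SAP says it follows, and the difference is not declared.

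The choice decides which events enter the main treatment-emergent, serious, special-interest and registry-disclosure tables. Two programmers working from this SAP could produce different counts and each point to a sentence in support. The days in dispute are also days on which adverse events are deliberately collected. Protocol 7.1 requires at least 14 days of monitoring after last dose, Protocol 5.6.1 schedules a contact at 14 days to ask about adverse events and SAEs, and SAP 1.1 keeps the 2-week safety follow-up.

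**Working it through.** The plan states no figure to reproduce. The check is a comparison of the texts followed by day counts.

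**1. Windows after last dose**

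| Source | Applies to | Days counted after last dose | Share of the protocol's 14 |
|---|---|---|---|
| Protocol 9.5.2 | all safety summaries | 14 | 14/14 = 100% |
| SAP 2.1.1 | safety summaries, adverse event tables by name | 0 | 0/14 = 0% |
| SAP 2.8.1 | treatment-emergent adverse events | 7 | 7/14 = 50% |
| SAP 2.8.3, 2.8.4.2 | laboratory data, vital signs | 7 | 7/14 = 50% |
| SAP 2.8.4.1 | ECG | 1 | 1/14 = 7.1% |

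The protocol's figure agrees with its own schedule: in Table 6-1 the last treatment visit is day 364 and the follow-up contact is day 364 + 14 = 378.

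**2. What happens to a single event**

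| Onset after last dose | SAP 2.1.1 | SAP 2.8.1 | Protocol 9.5.2 |
|---|---|---|---|
| Days 1-7 | out | in | in |
| Days 8-14 | out | out | in |

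**3. Is there a rule that settles it?** Neither SAP 2.1.1 nor 2.8.1 refers to the other's limit. SAP 2.8 bases its summaries mainly on on-treatment data without redefining the term, which leads back to 2.1.1. The introduction leads back to Protocol Section 9, that is, to 14 days. Section 4 is silent on safety windows.

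**4. Size in calendar time.** Let L be the days of treatment and w the days counted after last dose. The share of the protocol window left out is (14 - w)/(L + 14).

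For a 52-week completer, L = 364, and the windows are 364, 364 + 7 = 371 and 364 + 14 = 378 days:

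- SAP 2.1.1 (w = 0): 14/378 = 3.7%
- SAP 2.8.1 (w = 7): 7/378 = 1.9%

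SAP Section 4 says the study was terminated early, so many patients will have had shorter treatment. The documents give no exposure figures. With assumed durations:

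| Assumed exposure | Windows: +0 / +7 / +14 days | Left out by SAP 2.1.1 | Left out by SAP 2.8.1 |
|---|---|---|---|
| 26 weeks | 182 / 189 / 196 | 14/196 = 7.1% | 7/196 = 3.6% |
| 12 weeks | 84 / 91 / 98 | 14/98 = 14.3% | 7/98 = 7.1% |
| 4 weeks | 28 / 35 / 42 | 14/42 = 33.3% | 7/42 = 16.7% |

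**The case against.** The strongest reply is that the working rule is easy to find. SAP 2.1.1 is a section of general definitions, whereas Section 2.8 is the safety analysis plan, and there the adverse event, death-summary, laboratory and vital-sign sections all use 7 days. On that reading the live difference is 7 days against 14, and 2.1.1 needs only tidying. Seven days also has some support: Protocol 5.6.2, on contraception, equates one week with at least five half-lives of the drug. Nor need a collection period equal a summary period.

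Much of this is fair. Seven days is the most natural reading and might be defensible. But SAP 2.1.1 is not merely general: it names adverse event tables and treatment-emergent events, so it is as specific as 2.8.1. And if 2.8.1 prevails, the change from the protocol's 14 days is still neither declared nor justified; the SAP does not cite the half-life reasoning.

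Two limits on the harm also stand. No event is lost: all safety data are listed, those outside the on-treatment period are flagged, and some tables (the SAP does not say which) will cover everything recorded after dosing begins. The laboratory, vital-sign and ECG limits are clear in themselves. Because the week-54 contact is by telephone, they matter only if a clinic visit, such as one for treatment discontinuation, falls in the excluded days.

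**Conclusion.** The point holds. The SAP gives two conflicting rules for the same adverse event tables, and both depart from the protocol without saying so. The rules disagree about events starting 1-14 days after last dose. For a 52-week completer that is up to 3.7% of the protocol's window, or 1.9% if the 7-day rule is applied. The shares rise with shorter exposure, but the table of shorter durations rests on assumed values. All are shares of calendar time and do not estimate how many events would move. The laboratory, vital-sign and ECG limits are undeclared departures from the same protocol rule, with a smaller practical effect. Deaths are a named exception and are not in conflict. There is no evidence of bias between arms, and no hypothesis test is affected. It should be corrected because the content of the main safety tables must not depend on which SAP section was read.

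**What to change.** Define one safety window and use it in both SAP 2.1.1 and 2.8.1, stated as separate from the on-treatment periods used for efficacy. (SAP 2.7.2 ends the secondary-endpoint period at last dose plus 1 day, so one shared flag would not serve.) Set the safety window to the protocol's last dose plus 14 days, or keep a shorter one and declare and justify it in SAP Section 4. Handle the laboratory and vital-sign limits (7 days) and the ECG limit (1 day) the same way: align or declare. At most, bring the 7-day deaths summary in SAP 2.8.2 into line with the chosen window.

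The cost is SAP wording, one safety-window flag, and revised cut-offs in the laboratory, vital-sign and ECG programs. Adverse events are already collected for at least 14 days after last dose, so no new data are needed.

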2.8.1.1 Adverse events of special interest / grouping of AEs

The number and percentage of patients with treatment emergent adverse events of special interest will be summarized for each type of event with a break-down for each type of event by SMQ (when applicable) and preferred term. The Compound Case Retrieval Strategy (CRS) will be used to determine the MedDRA search criteria to be used to identify events of special interest.

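### Protocol 9.5.2 gives two conflicting rules for treatment-emergent adverse events; the SAP adopts the start-date-only rule without declaring that the worsening criterion was dropped

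*SAP*

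**What the plan says.** **Protocol 9.5.2 (Safety variables)** contains both rules.

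- An introductory paragraph says the adverse event (AE) tables will "summarize only on-treatment events, with a start date during the on-treatment period (treatment-emergent AEs").
- Under the Adverse events subheading, the TEAEs to be tabulated are events that started after first dose, or "events present prior to start of double-blind treatment but increased in severity based on preferred term". This governs the tables by system organ class and preferred term, by maximum severity, and by standardized MedDRA query.

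**SAP 2.1.1 (General definitions)** repeats the first rule nearly word for word: AE tables will "summarize only on-treatment events, with a start date during the on-treatment period, the so-called" treatment-emergent AEs.

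**SAP 2.8.1 (Adverse events)** defines TEAEs by start date alone: "Adverse events starting on or after the day of the first intake of study drug and until 7 days after the last intake". An event that begins between consent and the day of first intake "will be classified as prior adverse events and not included in tabulations of treatment emergent adverse events". The summaries that follow rest on this definition: "The number and percentage of patients who reported TEAEs will be summarized". The special-interest tables in SAP 2.8.1.1 carry the same limit ("patients with treatment emergent adverse events of special interest will be summarized"), and so do the disclosure tables in SAP 2.8.1.2.

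**SAP 4 (Change to protocol specified analyses)** declares only that the secondary endpoints become descriptive because the study was terminated early.

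**The concern.** AEs are collected from consent. Before Day 1 a patient passes through up to 2 weeks of screening and 4 or 10 weeks of run-in (Protocol 3.1), so some patients may be randomized with an AE still open. If such an event goes from mild to severe after dosing, one protocol sentence calls it treatment-emergent and the SAP calls it prior.

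The incidence and maximum-severity tables are at stake. Safety is a stated objective, and Protocol 3.6 lists headache, nausea, nasopharyngitis and dizziness among the potential effects of the drug. These are ordinary complaints that can begin during run-in. If the drug aggravates an existing complaint, the loss would fall more on the active arms and the tables would understate the difference from placebo.

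**Working it through.** No arithmetic applies. The plan states no figure on this point, and neither document gives a count of run-in AEs or of AEs that worsen on drug. The check applies each rule to the possible cases.

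| Case | Protocol 9.5.2, start-date sentence | Protocol 9.5.2, sentence with worsening | SAP 2.1.1 and 2.8.1 |
|---|---|---|---|
| Starts in run-in, severity unchanged on drug | Not counted | Not counted | Not counted |
| Starts in run-in, worsens on drug, one record with the run-in start date | Not counted | **Counted** | **Not counted** |
| Starts in run-in, worsens on drug, new record opened with an on-treatment start date | Counted | Counted | Counted |
| Resolves in run-in, recurs on drug at the same severity, new record | Counted | Counted | Counted |

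The SAP and the worsening sentence differ only in the second row. Whether that row occurs depends on how sites record a change in severity, and the documents leave this open:

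- Protocol 7.1 asks for a severity grade and start and end dates for each AE. It asks for no date of severity change and gives no rule for splitting a record.
- SAP 2.8.1.2 says how to count consecutive records of one preferred term, whatever their severity. It allows for split records but does not require them.
- Protocol 7.2.2 has progression of an initial serious event reported as follow-up to the original episode, which points towards one record. This concerns serious event reporting only.

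Where a second-row event would still be seen:

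- In the listings. SAP 2.8.1 lists all AEs after consent, and SAP 2.1.1 flags the pre-treatment ones.
- In the death table, if fatal. SAP 2.8.2 selects deaths by when they occur, not by when the AE began.
- Not in the TEAE, special-interest or disclosure tables. SAP 2.8 promises selected extra tables of data after first intake, but makes no provision for earlier events that worsen.

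Elsewhere the SAP does count worsening: SAP 2.8.4.1 tabulates newly occurring or worsening QTcF values, and SAP 2.8.4.2 does the same for notable vital signs.

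**The case against.** The strongest reply is that the SAP follows the protocol. The start-date sentence in Protocol 9.5.2 names the AE tables and carries the treatment-emergent label, and SAP 2.1.1 copies it. A reader might infer that the SAP departs from a clear protocol definition. The documents do not support that, because the protocol contradicts itself and the SAP chose one of its two rules. What remains is that the SAP made the choice silently, and the rule it dropped is the one attached directly to the listed AE tables.

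A reader might also infer that every run-in AE that worsens drops out of every AE table. That goes too far. A new record opened at worsening is counted, a fatal event enters the death table, and all events stay in the listings. A serious worsening may also be recorded as an event of its own, since the definition in Protocol 7.2.1 covers worsening of pre-existing conditions.

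The affected group is also narrower than all baseline complaints. Conditions present at consent go to medical history (Protocol 7.1) and are not in the SAP's prior class. Asthma is a poor example: an exacerbation before randomization makes the patient a failure (Protocol 4.2 and 5.5.4), and Protocol 6.5.2 counts an increase in asthma symptoms as a mild exacerbation.

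All of these limits stand. They narrow the point but do not remove the second row of the table.

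**Conclusion.** The point holds in a limited form. Protocol 9.5.2 contains two incompatible TEAE rules. The SAP adopts the narrower one and SAP 4 does not say so. As a result, a non-fatal AE that starts between consent and first intake, worsens on drug and is kept on its original record is absent from the incidence and maximum-severity tables.

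The size cannot be derived. It depends on how many patients reach Day 1 with an open AE, how many of those events worsen, and how many worsenings stay on one record; the documents give none of these. A reader might want to multiply guessed rates by 669, but that is the planned enrolment, and SAP 4 says the study was terminated early with insufficient follow-up for most patients. If sites always open a new record, the loss is nil.

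This should be corrected because the TEAE count otherwise depends on an unstated recording practice. It is not evidence that the AE tables are materially wrong. The length of the post-dose window, which also differs between Protocol 9.5.2, SAP 2.1.1 and SAP 2.8.1, is a separate matter.

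**What to change.** 1. **Protocol 9.5.2:** reconcile the two sentences so that one TEAE rule remains.
2. **SAP 2.1.1 and 2.8.1:** define a TEAE as either (a) any AE starting on or after first dose, including a recurrence at equal severity, or (b) an AE that started before first dose and has a higher severity recorded on or after first dose for the same preferred term. Derive (b) per patient and preferred term. Do not make a severity above the pre-dose level the whole test, because that would drop recurrences that (a) counts.
3. **Recording:** state that a severity increase after first dose is entered with its date, as a new record or as a dated severity change. Without this, (b) cannot be derived from a record that holds a single grade.
4. **Tables:** footnote the number of events counted only through worsening.

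If the sponsor prefers the start-date rule, declare in SAP 4 that the worsening criterion is dropped, and state how severity increases were recorded.

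The cost is wording in both documents and one derivation step, provided the dates of severity changes are available. AE percentages may rise slightly.
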